## **3 Study Objectives and Endpoints**

### **3.1 Primary Objective**

The primary objective is to determine if ticagrelor, compared to clopidogrel, can induce a greater measurable change in transcutaneous oxygen concentration (TcPO2), a surrogate for tissue perfusion, among advanced cases of CLI.

### **3.2 Study Endpoints**

#### **3.2.1 Primary Endpoint**

The primary endpoint is the absolute change in TcPO2 from baseline to month 6 compared between treatment groups.

#### **3.2.2 Secondary Endpoints**

- Rate of wound healing from baseline to month 6 in treatment groups for patients with Rutherford Classification Stage V-VI PAD
- Change in ankle-brachial index (ABI), toe-brachial index (TBI), toe-systolic pressure (TSP) and skin perfusion pressure (SPP) from baseline to month 6 in treatment groups
- Major adverse limb events including a composite of surgical limb loss or any major vascular repeat revascularization, including thrombectomy, thrombolysis, or major lower-extremity surgical procedure from baseline to month 6 in treatment groups
- Percent change in TcPO2 from baseline to 6 months
- Percent change and absolute change in TcPO2 from baseline to month 3 compared between treatment groups

A subgroup analysis will be performed among patients with non-gangrenous wounds to include a secondary assessment comparing TcPO2 to changes in SPP, ABI, TBI, and TSP between treatment groups at baseline and over the course of the study.

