## Study Synopsis

Title	Establishing the microcirculatory effects of ticagrelor on tissue perfusion in critical limb ischemia
Sponsor	[name]
Rationale	Ticagrelor has emerged as a novel P2Y12 adenosine receptor antagonist studied primarily in the treatment of coronary heart disease, but with properties that make the drug suitable for study in PAD. Beyond its antiplatelet effects, ticagrelor's ability to inhibit uptake of adenosine may provide cytoprotective and reparative properties that could prove therapeutic to patients with advanced PAD. Indeed, oral administration of ticagrelor to animals prevents contraction of vascular smooth muscle: an effect not seen with clopidogrel or prasugrel (5). Similar to effects seen with clopidogrel, ticagrelor may reduce leukocyte-platelet adhesion and improve microcirculatory function during ischemia by reducing blood viscosity (6). In addition to these beneficial antiplatelet effects, ticagrelor may provide additional benefit in smooth muscle relaxation by promoting serum adenosine concentrations.
Study Center	Cleveland Clinic and University Hospital in Cleveland
Indication	Rutherford Classification Stage IV through VI PAD
Study Objectives	
The primary goal of the proposed research is to determine if ticagrelor can induce a clinically significant change in transcutaneous oxygen concentration (TcPO2) superior to that induced by clopidogrel, among advanced cases of recently revascularized peripheral arterial disease (PAD).
 
Secondary objectives include:
 
 
1) to compare the rate of wound healing at 6 months between treatment groups among Rutherford Classification Stage V-VI patients
 
2) to determine if other markers of blood flow improve with treatment with ticagrelor.
 

Study Design	
This is a 2-arm randomized, active-controlled, pilot study. Patients over the age of 18 presenting with Rutherford Classification Stage IV-VI PAD will be included. Sixty (N=60) eligible patients who have given their consent to participate will be randomized to one of the following treatments:
 
 
• Clopidogrel (75 mg by mouth daily)
 
• Ticagrelor (90 mg by mouth twice daily)
 
 
All patients will be followed for 6 months after enrollment, with the primary endpoint assessed at 6 months after randomization.

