## **6 Study Procedures**

### **6.1 Screening/Baseline**

The following procedures will be performed on all patients at screening:

- Informed consent
- Demographics (see section 6.4.1)
- Medical History (see section 6.4.1)
- Rutherford Classification (see Appendix B)
- ABI, TBI, TSP

- Measurement of wound size if Rutherford Classification Stage V or VI
- Vital signs (B/P, HR, temperature, respirations)
- The results of the following will be recorded from local laboratory tests that were performed in the month prior to screening: BUN, crt, Hgb, Hct, plt, INR, PTT, HbA1c, Tchol, tg, LDL and HDL.
- Urine pregnancy test for females of childbearing potential
- Recent angiographic data
- TcPO2 measurement (see section 6.4.2)
- SPP measurement
- Concomitant medications
- Randomization
- Dispense study drug

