## **6.3 Month 6 follow up**

The patient will return to the clinic 6 months (180 days) after the date of randomization (+/- 2 weeks) and the following procedures will be performed:

- Rutherford Classification (see Appendix B)
- ABI, TBI, TSP
- Measurement of wound size and assessment of healing if Rutherford Classification Stage V or VI at Baseline
- Vital signs (B/P, HR, temperature, respirations)
- TcPO2 measurement

- SPP measurement
- Concomitant medications
- Assess study medication compliance
- Collect SAEs and AEs

Once a patient has been assessed at the 6-month follow-up visit they will exit the study. If ongoing use of ADP-receptor antagonist is required, patients will continue with either medication as indicated and approved although it will not be provided as part of the study. If no other indication exists for an ADP-receptor antagonist, either ticagrelor or clopidogrel will be discontinued, as per routine clinical practice.

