##### **6.4.1 Demographics and Medical History**

Demographic and medical history information to be collected include: age, race, gender, body-mass index, wound size, wound location, medical comorbidities including tobacco use history, duration of claudication, duration of lower extremity wound (if applicable), hypertension, hyperlipidemia, diabetes mellitus, prior cerebrovascular accident (CVA) or transient ischemic attack (TIA), carotid artery stenosis > 50%, chronic kidney disease (CKD), and complications related to prior PAD, such as prior wounds, forefoot amputation, below knee amputation, above knee amputation. Angiographic data relevant to revascularization procedures, including a record of arterial segment treated and vascular anatomy, will also be recorded.

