## **9 Statistical Plan**

### **9.1 Statistical Methods**

Baseline covariates will be compared with Fisher's exact test for categorical variables and two-sample t-test for continuous variables with a normal distribution or rank sum test if non-normally distributed between treatment groups. All comparisons between treatment groups will be performed as intent-to-treat using two-tailed significance testing at a value of 0.05.

Mixed model repeated measures analysis (MMRM) will be used to conduct the between-group comparison of absolute change in TcPO2 at 3 months and 6 months follow-up, with adjustment of baseline TcPO2 level following revascularization. Estimated within-group least squares (LS) means of TcPO2 and between-group differences of LS means in TcPO2 at 3- and at 6-month follow-up time points will be obtained from the MMRM modeling.

If the TcPO2 data is not normally distributed, the same MMRM method will be performed to analyze the rank transformed TcPO2 data, however the descriptive data is presented with median (interquartile range), and the between-group differences are shown using F statistics. Meanwhile, relevant nonparametric methods will be applied as sensitivity analysis. Friedman test will be conducted to compare the TcPO2 repeated measures from baseline to 6 months follow-up between the treatment groups. A Wilcoxon signed rank test will be used to assess intragroup change in TcPO2 at 3- and at 6-month follow-up.

The percent change in TcPO2 over time and other continuous secondary endpoints will be analyzed using the same strategies. Safety endpoints, adverse events and other categorical secondary endpoints will be analyzed using Fisher's exact test. The relationships between the primary endpoint of change in TcPO2 at 6 months follow-up and the continuous secondary endpoints will be explored by regression analysis.

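### The wound-healing endpoint has no stated type and no named baseline wound-size covariate, so a healed yes/no reading falls to an unadjusted Fisher's exact test

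*Combined protocol and SAP*

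**What the plan says.** Section 3.2.2 lists first among the secondary endpoints "Rate of wound healing from baseline to month 6 in treatment groups for patients with Rutherford Classification Stage V-VI PAD". The synopsis gives the matching objective: "to compare the rate of wound healing at 6 months between treatment groups among Rutherford Classification Stage V-VI patients". Neither says whether rate means the proportion healed, a time to healing, or a change in area.

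Section 9.1 offers two routes:
- **Continuous:** "other continuous secondary endpoints will be analyzed using the same strategies". The strategy referred to is the TcPO2 mixed model, fitted "with adjustment of baseline" TcPO2.
- **Categorical:** "Safety endpoints, adverse events and other categorical secondary endpoints will be analyzed using" Fisher's exact test.

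Wound size is collected at screening (section 6.1: "Measurement of wound size if Rutherford Classification Stage V or VI") and again at months 3 and 6 (section 6.3: "Measurement of wound size and assessment of healing if Rutherford Classification Stage V or VI at Baseline"). Section 6.4.1 also records how long the wound has been present. Section 4.2 describes 1:1 permuted blocks and names no stratification factor. No section names baseline wound size as a covariate.

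**The concern.** The primary endpoint is adjusted for its own baseline. The healing comparison is given no equivalent, although the natural baseline variable is already in the data set.

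Only patients with wounds at entry contribute, so the comparison rests on a subset of 60 patients. Appendix B spans digit ulcers (Stage 5) to severe ulcers or gangrene (Stage 6), so starting wounds may vary widely. If wound size predicts healing, ignoring it loses precision, and a chance difference in starting size between arms stays in the estimate. Section 9.1 compares baseline covariates between groups, but no adjustment follows from that comparison.

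The open endpoint type makes this worse. The analyst would choose both the measure and the covariate after the fact, in an open-label trial.

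**Working it through.** **Which route applies.** The Study Visits table lists wound size at all three visits and, as a separate row, assessment of healing at months 3 and 6 only. A status assessed only at follow-up has no baseline value of its own, which favours the categorical route. Wound size measured at three visits also fits the continuous route. Both readings are open.

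**The plan's own figure.** There is none for healing. The 90% power in section 9.2 concerns TcPO2 only.

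**Assumed inputs (none is in the documents).** 30, 40 or 50 wound patients in total, split equally; healing 40% v 72% overall; log baseline wound size standardised to z ~ N(0,1); logit P(healed) = a(arm) − slope × z, with slope 0.5 to 1.5; two-sided 0.05, as in section 9.1.

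**Fisher's exact test, calculated directly.** With m patients per arm, power = Σ Bin(a; m, 0.40) × Bin(b; m, 0.72) over all tables with p ≤ 0.05. This gives about 26%, 40% and 57% for m = 15, 20 and 25.

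**Three tests compared by simulation** (1,200 trials per cell; standard error at 50% power = √(0.25/1200) = 1.4 points). Ranges run over slopes 0.5 to 1.5:

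| Wound patients | Fisher | Firth, unadjusted | Firth, adjusted for log wound size |
|---|---|---|---|
| 30 | 25-26% | 39-42% | 41-52% |
| 40 | 40-42% | 51% | 58-67% |
| 50 | 58-60% | 65-66% | 66-77% |

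The unadjusted Firth column separates the two sources of gain.
- **40 patients, slope 1.0:** 40 / 51 / 59%. Leaving Fisher adds 51 − 40 = 11 points; the covariate adds 59 − 51 = 8.
- **30 patients, slope 1.5** (a separate run): 26 / 40 / 52%. Leaving Fisher adds 14; the covariate adds 12; the total is 26, the largest seen.
- **50 patients, low end:** the total is 66 − 60 = 6, of which the covariate gives 66 − 65 = 1.
- **40 patients, high end:** the covariate gives 67 − 51 = 16, the largest seen.
- **Slope 0 (wound size irrelevant):** adjusted Firth still beats Fisher by 13, 12 and 5 points at 30, 40 and 50 patients. All of that comes from leaving the exact test.

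Simulated type I error was 1.3-4.0% for Fisher and 3.8-5.6% for adjusted Firth.

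**Chance imbalance.** The difference between arms in mean z has SD √(4/n). At n = 40 this is 0.316, so the 95% limit is 1.96 × 0.316 = 0.62 SD. At that limit the odds ratio is multiplied by exp(slope × 0.62), which is 1.4 at slope 0.5 and 2.5 at slope 1.5. These are limits, not expected values. The chance of a difference above 0.5 SD is about 17% at 15 per arm and 11% at 20.

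**Continuous reading.** If the model adjusts for baseline wound size, nothing is lost. If it carries baseline TcPO2 over literally, wound size is left out. The text does not settle which.

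**The case against.** The strongest reply is that this is an unpowered secondary endpoint, in a subset of a pilot study, and that Fisher's exact test is valid as it stands. That is correct. Randomisation protects the unadjusted test, and its simulated error is below 5%. A reader might infer that chance imbalance in wound size biases the comparison or inflates false positives. It does not; it is a matter of precision.

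A reader might also infer that omitting wound size costs some 25 points of power. The documents supply none of the inputs, and even under favourable ones much of that gap belongs to Fisher's conservatism. That wound size predicts healing is itself an assumption here. The predictor that section 1.3 ties to wound healing by a threshold is TcPO2, at levels above 30 mmHg.

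A third tempting reading is that baseline wound size is left out whichever way the endpoint is read. That goes too far. Applying the same strategy to other continuous endpoints can naturally mean adjusting each for its own baseline. What stands is that the plan does not say so. Nor do the documents rank healing as the main clinical secondary endpoint. It is listed first, and major adverse limb events are listed as well.

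**Conclusion.** The plan leaves the type of the wound-healing endpoint undefined and names no baseline wound-size covariate. On the yes/no reading the comparison is unadjusted; on the continuous reading the covariate is ambiguous. Under the assumed inputs, the specified alternative gains about 6 to 26 points of power over Fisher, about 1 to 16 of them from the covariate. If wound size is not prognostic, the covariate's share is essentially zero. The absence of any named wound-size covariate rests on the text alone; the size of the gain rests wholly on assumption. The point concerns precision and prespecification, not validity, and is worth correcting because the correction is cheap.

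**What to change.** In section 9.1 and the synopsis:
- State what the healing endpoint is, and that it is compared at month 6 in patients who were Stage V-VI at baseline.
- For healed yes/no, specify Firth penalised logistic regression with terms for treatment and log baseline wound size. Report the odds ratio and the adjusted risk difference, each with a 95% confidence interval, and keep Fisher's exact test as supportive.
- If wound size is also analysed as continuous, state that its own baseline is the covariate.

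The cost is one paragraph, settled before outcome data are examined, with no new measurements. The drawback is that the odds ratio becomes conditional on wound size, which is why the adjusted risk difference should stand beside it.

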## **4 Selection and Withdrawal of Patients**

### **4.1 Study Population**

Approximately 60 patients who meet all inclusion criteria and no exclusion criteria will be randomized into the study.

Enrollment into the study will require severe symptomatic CLI without wounds (Rutherford Stage IV) or CLI with concomitant vascular insufficiency wounds (Rutherford Stage V-VI PAD).

Potential participants will be identified and screened prior to discharge or at the time of the first out-patient visit (within 2 weeks after discharge) after a percutaneous lower extremity arterial angiography with arterial intervention (stent or balloon angioplasty) for the presence of lower extremity vascular insufficiency. Participants will be classified as Rutherford Class IV – VI (with or without ulcerations). Per SOC, patients will have been placed on clopidogrel after the arterial intervention.

#### **4.1.1 Inclusion Criteria**

Eligible patients will be considered for inclusion in this study if they meet all of the following criteria:

1. Adults age 18-100 years with Rutherford Classification Stage IV through VI PAD with a recent percutaneous lower extremity arterial angiography with arterial intervention in the past 2 weeks
2. Willingness to sign informed consent
3. Ability to return for follow-up visits
4. A female patient of childbearing potential who is sexually active must agree to use adequate contraception from screening until 30 days after receiving the last dose of study drug. Women NOT of child bearing potential are defined as those who have been surgically sterilized (hysterectomy, bilateral oophorectomy, or tubal ligation) or who are postmenopausal (defined as at least 2 years since last regular menses). The female patient should not be lactating and must have a negative pregnancy test at screening.

#### **4.1.2 Exclusion Criteria**

Patients will be ineligible for this study if they meet any one of the following criteria:

1. Intolerance to thienopyridines
2. Hypersensitivity to ticagrelor or any component of the product
3. Concomitant use of oral anticoagulation with vitamin K antagonist, factor Xa inhibitor, or direct thrombin inhibitor
4. History of intracranial hemorrhage
5. History of severe hepatic impairment defined by baseline transaminase greater than or equal to 3x ULN or any elevation in bilirubin
6. Active bleeding
7. Allergy to aspirin
8. Baseline TcPO2 < 10 mmHg post angiography
9. Resting pre-procedure heart rate < 50 beats-per-minute without a permanent pacemaker and not on an atrioventricular nodal blocking agent
10. Severe COPD on home oxygen therapy
11. Patients on strong CYP3A inhibitors and/or CYP3A inducers that cannot be stopped for the course of the study. \*

- \* Strong inhibitors of CYP3A are the following medications: ketoconazole, itraconazole, voriconazole, clarithromycin, nefazodone, ritonavir, saquinavir, nelfinavir, indinavir, atazanavir and telithromycin.  
Potent inducers of CYP3A include the following medications: rifampin, dexamethasone, phenytoin, carbamazepine and phenobarbital.  
In addition, ticagrelor will result in higher serum concentrations of simvastatin and lovastatin because these drugs are metabolized by CYP3A4 and doses greater than 40 mg with these medications should be avoided.

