### **5 Treatment of Patients**

#### **5.1 Treatment Regimen**

Patients are placed on clopidogrel after their arterial intervention per SOC. They will remain on clopidogrel up to the time that randomization occurs. For patients that are randomized to ticagrelor, the clopidogrel will be stopped.

Study Drug	Dose Level and Frequency
clopidogrel	75 mg by mouth daily
ticagrelor	90 mg by mouth twice daily

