## **7 Pharmacologic Loading Pre-revascularization**

For patients requiring revascularization, pharmacologic loading of an ADP-receptor antagonist will have been ordered as per standard of care so as to minimize risks for post-procedural arterial thrombosis. For this study, patients will have been treated with clopidogrel up to, during, and immediately after the time of revascularization as is standard of care. After revascularization, an ADP-receptor antagonist (e.g., clopidogrel) is routinely continued for 6 months, and then discontinued. Patients will be screened and randomized for the study either in the hospital after the procedure prior to discharge or at the time of the first out-patient clinic visit following revascularization (approximately one to two weeks after the procedure). Patients will be randomized to either clopidogrel or ticagrelor. After randomization patients will receive study medication (ticagrelor) with a 90-day provision through 6 months follow-up, refilled at the 3 month clinic visit.

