## **8.5 Safety Monitoring**

Safety endpoints to be assessed include major bleeding and self-reported dyspnea and self-reported symptomatic bradycardia. Major bleeding is defined as a composite of fatal bleeding, intracranial bleeding, hypovolemic shock or severe hypotension due to bleeding requiring pressors, or need for transfusion of at least 2 units in any 24-hour period. Self-reported symptomatic bradycardia is defined as self-reported symptoms of shortness of breath, chest discomfort, or dizziness with a confirmed heart rate of < 45 bpm at the time of the symptoms.

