## **11 Data Handling and Record Keeping**

### **11.1 Data Collection**

Data will be collected by the Nurse or Site Coordinator or designee. Data sources include patient reports and available medical records, including those from electronic medical record. Values for preoperative variables will be selected nearest to the date of the revascularization procedure, but used only if they were obtained within 30 days of the procedure.

C5Research Data Management will create a Case Report Form to document the agreed upon variables to be captured in the REDCap database.

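### Minor: exclusion 9 applies its 50 bpm limit only to the heart rate before revascularization, although a current rate is recorded at the visit where the patient is randomized

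*Combined protocol and SAP*

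**What the plan says.** Exclusion 9 in section 4.1.2, with the same wording in the synopsis, reads: "Resting pre-procedure heart rate < 50 beats-per-minute without a permanent pacemaker and not on an atrioventricular nodal blocking agent". No other inclusion or exclusion criterion sets a limit on heart rate.

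Inclusion 1 in section 4.1.1 requires a "recent percutaneous lower extremity arterial angiography with arterial intervention in the past 2 weeks". Section 7 gives the order of events: "Patients will be screened and randomized for the study either in the hospital after the procedure prior to discharge", or else at the first outpatient visit, about one to two weeks after the procedure. Until randomization every patient takes clopidogrel. Section 5.1 then states: "For patients that are randomized to ticagrelor, the clopidogrel will be stopped".

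The baseline list in section 6.1 includes "Vital signs (B/P, HR, temperature, respirations") and, further down the same list, randomization and the dispensing of study drug. The Study Visits table shows the same.

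Section 8.5 names the safety endpoints: "Safety endpoints to be assessed include major bleeding and self-reported dyspnea and self-reported symptomatic bradycardia". Sections 8.1 and 8.5 define symptomatic bradycardia as shortness of breath, chest discomfort or dizziness together with a confirmed rate below 45 bpm.

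**The concern.** An entry limit on heart rate is most useful when it describes the patient at the time exposure to the new drug begins. Here the limit is tested on a value from before the leg intervention, while a value from the day of randomization is collected and left out of the eligibility decision. The protocol gives no reason for the choice.

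Two things are at stake, both small. The first is entry safety: a patient who is below the sponsor's own threshold on the current reading, with neither exempting condition, can start ticagrelor. The second is how one safety endpoint reads. The symptomatic bradycardia definition asks for symptoms with a rate below 45 bpm and does not ask for a fall from baseline. A patient already below 45 bpm at randomization would therefore need only a qualifying symptom, at an unchanged rate, to be counted as an event.

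**Working it through.** The plan states no figure to reproduce. The check sets the relevant provisions side by side and adds simple day arithmetic.

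1. **What the procedure means.** Sections 7 and 11.1 use the term for the revascularization. Section 6.4 also calls the TcPO2 and SPP measurements study procedures, so the phrase in exclusion 9 could be read as meaning before those measurements. That reading is strained, given the usage elsewhere.

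2. **Interval from procedure to randomization.** Inclusion 1 allows at most 2 weeks = 14 days. A patient randomized in hospital before discharge can be near 0 days. The range is therefore 0 to 14 days, and about 7 to 14 days by the outpatient route in section 7. Section 4.1 describes the outpatient visit as within two weeks of discharge, which could run later, but inclusion 1 counts from the intervention and so sets the limit.

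3. **Age of the tested value.** For a heart rate taken on the day of the procedure, the age at randomization equals the interval in step 2: 0 to 14 days.

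4. **Is a current value available?** Yes. Section 6.1 and the Study Visits table place heart rate and randomization at the same visit. Neither section 4.1.1 nor section 4.1.2 refers to that value.

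5. **Who passes as written?** Take hypothetical patients with no pacemaker and no AV nodal blocker, who meet all other criteria.
   - 52 bpm before the procedure, 47 bpm at screening: exclusion 9 tests 52, and 52 ≥ 50, so the patient is eligible.
   - 52 bpm before the procedure, 44 bpm at screening: exclusion 9 again tests 52, so the patient is eligible. Since 44 < 45, the heart-rate part of the symptomatic bradycardia definition is met before the first dose.

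6. **Does anything else close the gap before entry?** Drug discontinuation after a serious adverse reaction (section 4.3), collection of bradycardia events (section 8.1) and review by the Medical Monitor (section 10.2) all respond to events after randomization. The next scheduled vital signs are at month 3.

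7. **Does the protocol tie any criterion to the state after the procedure?** Yes. Exclusion 8, directly above, uses the TcPO2 measured after angiography.

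The number of patients affected cannot be calculated, because the documents give no distribution of heart rate at either time.

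**The case against.** The strongest reply is that this is a choice, not an error. Exclusion 9 is workable and contradicts nothing. Its two exemptions suggest that it aims at unexplained, intrinsic bradycardia, and for a standing trait a resting value before the intervention is a reasonable marker. The protocol gives no reason for its other exclusions either. Nothing in the documents suggests that heart rate falls between leg angioplasty and randomization. The investigator sees the screening rate before randomizing and may decline to enroll. Recruitment is also slow: 60 patients over 48 months is 60 / 48 = 1.25 per month, so even a few extra exclusions matter.

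Most of this stands, and it is why the point is minor. It does not remove the gap: clinical discretion is not a written criterion, and the later safeguards do not act at entry.

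Three stronger readings are tempting, and the documents do not support them.

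- **A reader might put the age of the heart-rate value at up to 30 + 14 = 44 days**, because section 11.1 says preoperative values are "used only if they were obtained within 30 days of the procedure". That sentence is a data-collection rule. It does not mention heart rate or eligibility, and it selects the value nearest the procedure. The supportable range is 0 to 14 days for a value from the procedure day.
- **A reader might say the limit was set to protect the bradycardia endpoint.** No section links exclusion 9 to section 8.5. The connection is a plausible inference and no more.
- **A reader might infer that a rate below 50 bpm at screening is dangerous on ticagrelor.** The protocol admits slower patients who take an AV nodal blocker or have a pacemaker, so 50 bpm is not an absolute line. An asymptomatic patient at 45 to 49 bpm does not meet the endpoint definition. For drug-specific information the protocol refers to the Investigator Brochure, which is not among these documents.

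**Conclusion.** The point holds as an inexpensive improvement to entry safety. The only heart-rate criterion tests a pre-procedure value, randomization comes 0 to 14 days after the procedure, and the current rate recorded at that visit plays no part in eligibility.

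The conclusion rests on two readings: that the procedure in exclusion 9 is the revascularization, and that the two-week limit in inclusion 1 governs. That the added check would also give a cleaner reading of the symptomatic bradycardia endpoint is inference. No harm is shown and no frequency can be given. The TcPO2 endpoint, the sample size and the planned analyses do not depend on it.

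**What to change.** In exclusion 9, in section 4.1.2 and in the synopsis, apply the limit to a resting heart rate below 50 bpm either pre-procedure or at the screening visit before randomization. Keep the pre-procedure test, the threshold and both exemptions, so that patients with a permanent pacemaker or on an AV nodal blocker remain eligible. Because section 6.1 does not say that the screening rate is taken at rest, the new wording should say so.

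The cost is one phrase in two places. No visit, test or analysis is added, since vital signs are already scheduled. The downside is possibly a very few additional exclusions, including a patient with a single low reading soon after an in-hospital procedure. If the sponsor prefers the pre-procedure value alone, one sentence giving the reason would settle the point.
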